- (H3) completion rates for daily activities will be similar to previous web-based interventions.

Aim 4 (Assess the impact of the intervention on learning and symptoms)

- (H4) participants will show significant learning as evidenced by increases in correct responses to knowledge questions from baseline to post
- (H5) participants in the intervention condition will evidence less high-risk drinking and PTSD at 3-month follow-up than participants in the assessment-only condition.

8. Description of trial design

Type of trial

(eg, parallel group, crossover, factorial, single group)

Parallel group, two arm

Allocation ratio

1:1

Framework

(eg, superiority, equivalence, noninferiority, exploratory)

Superiority

Methods: Participants, Interventions, and Outcomes

9. Study setting

Description of study settings

Although the intervention will be conducted online, participants will be recruited from the Seattle–Tacoma–Bellevue, WA Metropolitan Statistical Area (defined by the US Census Bureau). According to the [2018 American Community Survey](#), this represents 3,939,363 people. The median age of the population in this area is 37, and the population is 50% female. The population is 62% White, 14% Asian, 10% Hispanic, 6% Black, 6% two or more races/ethnicities, and 2% other. The median per-capita income is \$46,204, and the median household income is \$87,910. The majority of individuals in this area (92.9%) are high-school graduates, and 43.6% have a bachelor's degree or higher.

Reference to where list of study sites can be obtained

N/A

10. Eligibility Criteria

Inclusion criteria

- Informed consent
- Self-identification as female
- Sexual assault, defined as endorsement of unwanted, attempted or completed sexual contact in the past 10 weeks on the Sexual Experiences Survey- Revised
- Age ≥ 18
- English fluency
- Telephone and internet access for 3 months
- Consumption of ≥ 1 alcoholic drink in the past month
- ≥ 1 episode of high-risk drinking in past 6 months, defined as either more than 3 drinks on a given day or more than 7 drinks in a given week
- At least 3 symptom clusters endorsed on the PTSD Checklist

Inclusion criterion	How assessed at phone screening	How confirmed at baseline
Informed consent	Verbal consent	Electronic consent
Self-identification as female	Single item	N/A
Age ≥ 18	Single item	N/A
Past-10-week sexual assault history	
• “Have you experienced unwanted sexual	N/A

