Strategies for achieving adequate participant enrollment to reach target sample size

Participants will enter the trial through one of 4 routes. In general, regardless of recruitment route, the intervention will be described as a way to monitor their symptoms and build coping skills. Potential participants will be informed that all eligible participants will receive symptom monitoring, some participants will receive coping skills immediately, and some will be offered the coping skills in 3 months.

1. HATC “call-back list”- Clients who independently (i.e., not via referral through the emergency department) contact HATC within 10 weeks of an assault requesting a therapy appointment will be provided a brief study description and the study phone number over the phone by the HATC social worker.
2. Sexual assault survivors presenting for care at the emergency department- Approximately 2-25 individuals per week present to Seattle-area emergency departments for care related to a recent sexual assault. HATC social workers attempt to follow up with all survivors over the phone and schedule in-person follow-up sessions with a social worker ([name]) and a SANE ([name]) for 1-2 weeks post-assault. Survivors will be told about the study during the scheduling phone call and again at the in-person session, and will be given the study phone number.
3. Emails to University of Washington registered students- We will request the registrar’s list for all 3 campuses each quarter. Participants who have asked not to be contacted or who have already participated will be removed from the list.
4. Community flyers and advertisements- We will post on the Seattle Craigslist page, on Facebook targeting Seattle-area women, and at the King County Sexual Assault Resource Center in Renton.

Methods: Assignment of Interventions (for Controlled Trials)

16. Allocation

16a. Sequence generation

Method of generating the allocation sequence (eg, computer-generated random numbers) and list of any factors for stratification. To reduce predictability of a random sequence, details of any planned restriction (eg, blocking) should be provided in a separate document that is unavailable to those who enroll participants or assign intervention.

Participants will be randomly assigned to intervention or control via a computer-generated randomization schedule. Randomization will not be stratified.

16b. Allocation concealment mechanism

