Randomization will occur without human involvement; therefore, no allocation concealment method will be needed.

16c. Implementation

Who will generate the allocation sequence, who will enroll participants, and who will assign participants to interventions

Participants will be preliminarily screened for the study over the phone by a study staff person. The staff person will then give them a web link to complete the baseline survey. Participants will then complete the baseline survey online by themselves, which will confirm eligibility. Participants will not be able to retake the baseline survey. At the end of the survey, they will be informed of their eligibility status, and if eligible, intervention condition (randomization will occur within the survey), and be directed to log into the app.

17. Blinding (masking)

17a. Who will be blinded after assignment to interventions (eg, trial participants, care providers, outcome assessors, data analysts), and how

Due to the nature of the intervention, neither participants nor study staff can be blinded to allocation. Baseline and follow-up assessments will occur via self-report; thus, no blinding of staff assessors is needed.

17b. If blinded, circumstances under which unblinding is permissible, and procedure for revealing a participant's allocated intervention during the trial

N/A

Methods: Data Collection, Management, and Analysis

18. Data collection methods

18a. Plans for assessment and collection of outcome, baseline, and other trial data

Participants will complete online self-report surveys at baseline, daily during the intervention, post-intervention, and 3-month follow-up. Participants will be paid \$20, \$40, and \$60 for participation in baseline, post-intervention, and 3 months post-baseline surveys, respectively. Participants will be paid \$3 per day of survey completion (daily participation will be incentivized to make daily data analysis possible) and \$10 bonus for completion of 7 consecutive days. Baseline, post-intervention, and 3-month assessments will take approximately 30 minutes to complete, and daily assessments will take approximately 5 minutes. Baseline and post-intervention surveys will assess immediate intervention effects, and 3-month follow-up will assess long-term maintenance of effects. Post-intervention and 3-month follow-up assessments will assess changes in learning (i.e., increases in correct responses to items reflecting knowledge about intervention concepts) and symptoms.

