
18b. Plans to promote participant retention and complete follow-up

List of any outcome data to be collected for participants who discontinue or deviate from intervention protocols

The following steps will be taken to promote retention:

- We will collect extensive contact data from participants and attempt to reach them for all follow-up assessments unless directed otherwise.
- The daily surveys will be accessed from within the app, which is intended to increase the likelihood that participants complete both surveys and activities
- Participants can opt in to receive a text from the app prompting them to complete a survey.
- Participants will be paired with a coach, who will remind them to complete baseline and post-intervention surveys
- Participants will receive reminders from study staff to complete the baseline, post-intervention, and 3 month surveys.
- Participants will be paid \$3 per day of survey completion (daily participation will be incentivized to make daily data analysis possible) and \$10 bonus for completion of 7 consecutive days. Participants will be paid \$20, \$40, and \$60 for participation in each assessment (at baseline, termination, and 6 3 months post-termination), respectively. Total possible remuneration will be \$213 for both conditions. Participants will be paid for each survey and assessment they complete, even if they do not complete all assessments.
- The screener will emphasize the importance of completing both daily surveys and daily intervention tasks if assigned to the intervention.
- The screener will instruct participants to complete the baseline survey once they terminate the phone call.

19. Data management

Plans for data entry, coding, security, and storage

Including any related processes to promote data quality (eg, double data entry; range checks for data values). Reference to where details of data management procedures can be found, if not in the protocol.

Entry and coding

Data will be completely digital; no data entry will be needed. In some cases, scale scores will be automatically calculated by custom programming. When this does not occur, the first author will create SPSS syntax and a data dictionary referencing scoring procedures.

Security and storage

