web-based interventions (H3) will be tested via descriptive statistics, visualizations, and multilevel models; 95% CIs will determine whether the number of days completed is significantly different from 10 and the percent of days completed is significantly different from 71.43%.

Relevant to Aim 4 (Assess the impact of the intervention on learning and symptoms), as this study was not powered to detect all effects of interest, we rely primarily on the direction and magnitude of effect sizes to interpret results and conduct significance tests in an exploratory manner. The hypothesis that participants will show significant learning as evidenced by increases in correct responses to knowledge questions from baseline to post (H4) will be tested via paired-samples t-tests. The hypothesis that participants in the intervention condition will evidence less high-risk drinking and PTSD at 3-month follow-up than participants in the assessment-only condition (H5) will be tested via mixed-effects models. Because they are non-negative discrete integers that typically show a positive skew, Poisson or negative binomial distributions will be examined. Dummy variables for the intervention condition with the control as the reference will be included. We will examine time by condition interactions to assess effects at each follow-up.

20b. Methods for any additional analyses

(eg, subgroup and adjusted analyses)

We may include additional covariates to increase precision or if there is evidence that randomization did not adequately balance covariate distributions by condition.

20c. Analysis population and missing data

Definition of analysis population related to nonadherence (eg, as randomized analysis), and any statistical methods to handle missing data (eg, multiple imputation)

We will use an intent to treat analysis, in which participants will be retained in the group to which they were originally randomized. Outcome data from all participants will be included in analyses. We will also explore the use of randomization-based efficacy estimators (White, 2005). We will use maximum likelihood estimation for missing data.

Methods: Monitoring

21. Data monitoring

21a. Data monitoring committee

Composition of data monitoring committee (DMC)

N/A

Summary of its role and reporting structure

N/A

Statement of whether it is independent from the sponsor and competing interests

Reference to where further details about its charter can be found, if not in the protocol

N/A

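### H4 (learning) is analysed only as a baseline-to-post change with no arm named, so it does not estimate the intervention's impact on learning that Aim 4 asks for

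*Combined protocol and SAP*

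**What the plan says.** Section 7 sets Aim 4 as "Assess the impact of the intervention on learning and symptoms". Under it, H4 reads "participants will show significant learning as evidenced by increases in correct responses to knowledge questions from baseline to post". H4 names no arm and no comparator. H5, under the same aim, names both: "participants in the intervention condition will evidence less high-risk drinking and PTSD at 3-month follow-up than participants in the assessment-only condition".

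Section 20a gives one method for H4: "increases in correct responses to knowledge questions from baseline to post (H4) will be tested via paired-samples t-tests". The condition dummies and the time-by-condition interactions come later in that paragraph, after H5, its mixed-effects models and the sentence on Poisson or negative binomial distributions. For Aim 4 as a whole, 20a says "we rely primarily on the direction and magnitude of effect sizes to interpret results" and treats significance tests as exploratory.

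On data collection, section 18a says "Post-intervention and 3-month follow-up assessments will assess changes in learning (i.e., increases in correct responses to items reflecting knowledge about intervention concepts") and does not limit this to one arm. Section 14 plans 20 participants per arm and says the control group is there to supply pilot effect sizes.

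**The concern.** The trial is randomised 1:1 with a control arm, yet the stated learning analysis does not use that arm as a comparator. A baseline-to-post change mixes what the intervention adds with what participants would gain anyway, for example from seeing the same questions twice. Because no arm is named, three readings are open:

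- Intervention arm only: the change includes any gain controls would also show.
- Both arms pooled: it includes that gain and also halves the intervention's effect.
- Each arm separately: it gives two changes, with no stated comparison between them.

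None of these gives the intervention's effect in general. Since the plan leans on effect sizes more than p-values, the effect size itself is what is affected. The pilot figure carried forward for learning would depend on an unstated choice of arm and could not be read as impact.

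**Working it through.** **The plan's own figures.** The documents give no effect size, correlation or power for knowledge. The 0.80 power in section 14 concerns RAPI drinking counts and has no bearing on H4.

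**Do controls take the post survey?** Section 18b states a maximum payment of 213 dollars for both conditions. The inputs are 20, 40 and 60 dollars for the three assessments, 3 dollars per daily survey over 3 weeks, and 10 dollars per 7 consecutive days:

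20 + 40 + 60 + 21 × 3 + 3 × 10 = 213.

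Without the 40 dollars for the post survey the total is 173. So both arms take the post survey. This does not show that both answer the same knowledge items.

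**Are controls a suitable comparator?** Section 15 tells candidates that "some participants will receive coping skills immediately, and some will be offered the coping skills in 3 months". Controls have therefore not been offered the skills when the post survey is taken.

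**What each analysis estimates** (d and g in baseline SD):

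- Paired change, intervention arm: g + d.
- Paired change, pooled 1:1: 0.5(g + d) + 0.5g = g + d/2.
- Between-arm difference at post, adjusted for baseline: (g + d) − g = d.

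If g = 0, the intervention-arm change is unbiased, but the pooled change is still half of d.

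**Illustration.** Assumed: d = 0.5, baseline-to-post correlation ρ = 0.6, 20 per arm, no loss. Each cell gives the expected estimate and the share of 95% CIs that contain d. Intervention-arm coverage uses a noncentral t with 19 df and noncentrality g√20/√(2(1−ρ)), which is 5g at ρ = 0.6. The other columns come from 20,000 simulated trials.

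| g | Intervention arm, paired | Pooled, paired | Between arms, adjusted |
|---|---|---|---|
| 0 | 0.50; 95% | 0.25; 62% | 0.50; 95% |
| 0.1 | 0.60; 92% | 0.35; 84% | 0.50; 95% |
| 0.3 | 0.80; 70% | 0.55; 94% | 0.50; 95% |
| 0.5 | 1.00; 34% | 0.75; 63% | 0.50; 95% |

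The pooled 94% at g = 0.3 is a coincidence: g + d/2 = 0.55 happens to lie near d. Over ρ = 0.5 to 0.7, intervention-arm coverage is 92–93%, 62–75% and 22–44% at g = 0.1, 0.3 and 0.5.

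**If the intervention does nothing** and everyone gains 0.3 SD, a two-sided 5% paired t-test shows a significant increase in 25–38% of trials in one arm (n = 20) and in 46–67% pooled (n = 40), for ρ = 0.5 to 0.7.

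**Precision given up.** 95% CI half-widths in SD units:

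- Paired: t(n−1) × √(2(1−ρ)/n). At n = 20, ρ = 0.6: 2.093 × 0.200 = 0.419.
- Between arms: t(2n−3) × √(1−ρ²) × √(2/n). At n = 20, ρ = 0.6: 2.026 × 0.8 × 0.316 = 0.513.

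The pairs (paired, between) are 0.47 and 0.56 at ρ = 0.5, and 0.36 and 0.46 at ρ = 0.7. With 16 per arm (an assumed 20% loss) and ρ = 0.6 they are 0.48 and 0.58.

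**The case against.** The strongest reply is that the test fits the hypothesis. H4 is worded as a within-person increase, and a paired t-test answers that. H1 to H3 use the same shorthand and can only mean intervention users, so H4, which concerns intervention concepts, most naturally means the intervention arm; pooling is then the least likely reading. Aim 4 tests are exploratory, and section 14 says the sample size was set for practical reasons.

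Most of this stands, and it limits the weight of the point. It does not remove it. On the intervention-arm reading the estimate is still g + d, and the exploratory label covers significance tests, not the effect sizes on which the plan relies. Pooling also cannot be excluded, because 20c says all participants' outcome data enter the analyses.

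A second reply is about accuracy. At ρ = 0.6 and 20 per arm the variances are 0.040 (paired) and 0.064 (between arms), so the intervention-arm change has the smaller mean squared error for d when g is below √0.024, about 0.15 SD. The limit is much the same at ρ = 0.5 and 0.7. This is correct, but without the control arm nobody can tell whether g is that small.

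Third, the magnitudes are assumed, and the 34% coverage needs g as large as d. That is fair; at g = 0.1 coverage is close to nominal.

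Last, section 12 defers outcomes to the registry, and the participant timeline is not readable in the text available. Either might say who answers the knowledge items. The fix is therefore conditional.

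**Conclusion.** The concern holds. For knowledge, the plan states only a paired baseline-to-post test, with no arm and no between-arm contrast, while the aim is the intervention's impact on learning. The bias as an estimate of d is g in the intervention arm and g − d/2 when pooled. Its actual size is unknown because the documents give neither g nor d. It is zero in the intervention arm if controls would gain nothing. With d = 0.5, a control gain of 0.3 SD would turn an expected 0.50 into 0.80. The illustrations assume 1:1 allocation, 20 per arm, equal variances and correlations of 0.5 to 0.7.

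The plan should be changed, but this is a cheap improvement in a small pilot, not a defect that invalidates the trial. Confidence is medium, because the documents do not confirm that controls answer the same items.

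**What to change.** Amend section 20a as follows:

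1. Name the arm or arms to which the H4 paired change applies.
2. State whether both arms answer the same knowledge items at baseline and post. If they do, make the H4 estimate the between-arm difference in post score adjusted for baseline, with a 95% CI, in all randomised participants. Fitting baseline and post scores jointly by maximum likelihood, with a common baseline mean, fits the missing-data approach in 20c and keeps participants who lack a post score.
3. Report the paired change in each arm as descriptive.
4. If controls do not answer the items, say that H4 is descriptive and cannot show intervention impact.

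The cost is one or two sentences and apparently no new data. The downside is the wider interval shown above, so the result should be presented as a pilot estimate. At 20 per arm, 80% power would need a difference of roughly 0.77 SD at correlation 0.5 or 0.63 SD at 0.7 (normal approximation, two-sided 5%).

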Given evidence that human contact increases adherence to app interventions, we will provide participants in both conditions with ongoing phone coaching. All screened participants, regardless of randomization or condition, will get one phone or Zoom call from a coach to ensure that app installation and onboarding were successful (if randomized), answer questions (for all participants), encourage adherence to surveys (if randomized), and provide resources (if not randomized). This call will be scheduled during the phone screening and will occur within 3 business days of screening. The coach will be informed of the individual's condition before the call.

Participants in both conditions will be offered three additional weekly phone/text/Zoom check-ins with their coach to troubleshoot progress and skill application (intervention condition only), check in on overall well-being (both conditions), encourage daily survey completion (both conditions), monitor risk (both conditions), and troubleshoot technical difficulties (both conditions). Coaches will be able to access participant data (e.g., activity data, time spent in the app, self-report data) prior to the weekly appointment.

[figure not shown]
11d. Relevant concomitant care and interventions that are permitted or prohibited during the trial

Participants will not be restricted from accessing any care or interventions during the course of the trial. It is likely that individuals recruited from the Harborview Center for Sexual Assault and Traumatic Stress (a primary recruitment site) will receive treatment for sexual-assault-related distress while enrolled in the study.

12. Outcomes

See ClinicalTrials.gov.

13. Participant timeline

14. Sample size

Estimated number of participants needed to achieve study objectives

$n = 20$ in intervention condition; $n = 20$ in control condition

How sample size was determined

Including clinical and statistical assumptions supporting any sample size calculations

The study was designed to collect information about feasibility; thus, the sample size was set for practical reasons rather than detecting effect sizes or significance testing. A control group was included to obtain pilot estimates of effect sizes, and we will have

statistical power of 0.80 to detect an effect size of count ratio of 1.40, based on a mean base rate RAPI drinking problems count of 6 in untreated women from a preliminary study (R21AA016211 PI: [name]).

15. Recruitment

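### The H4 paired t-test uses only women with both a baseline and a post-intervention knowledge score, which does not fit section 20c's all-participant, maximum-likelihood rule

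*Combined protocol and SAP*

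**What the plan says.** Section 20a, under Aim 4, states that "increases in correct responses to knowledge questions from baseline to post (H4) will be tested via paired-samples t-tests". It does not say what happens when the post score is missing, or whether the test uses the intervention arm or both arms.

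Section 20c (analysis population and missing data) states: "Outcome data from all participants will be included in analyses". It adds: "We will use maximum likelihood estimation for missing data". Neither sentence is limited to a particular hypothesis.

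The other Aim 4 hypothesis has a method that can follow 20c: the comparison of the intervention condition with women in the other arm, "than participants in the assessment-only condition (H5) will be tested via mixed-effects models".

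Knowledge is also collected after the H4 window. Section 18a says: "Post-intervention and 3-month follow-up assessments will assess changes in learning". For Aim 4 as a whole, section 20a says that "we rely primarily on the direction and magnitude of effect sizes to interpret results and conduct significance tests in an exploratory manner".

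**The concern.** A woman with no post-intervention score has no within-person difference. The paired t-test drops her, including the baseline score that the trial already holds, and it has no maximum-likelihood step. The method named for H4 therefore cannot carry out the general rule in 20c whenever a post survey is missing. Some missing surveys are foreseeable: section 18b pays for each completed assessment even when others are missed.

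What is at stake is the size of the estimated learning gain. Aim 4 is to be read mainly from effect sizes, so calling the significance tests exploratory does not protect the quantity that selective loss of pairs would distort. A woman who misses the post survey but answers at 3 months has two knowledge scores, and neither enters the H4 test.

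**Working it through.** **The plan's own power figure.** Section 14 gives power 0.80 for a count ratio of 1.40 on a base count of 6, with 20 per arm. With Poisson variance, two-sided 5% (assumed) and no missing data, SE = sqrt(1/(20×6) + 1/(20×8.4)) = 0.1195 and ln 1.40 = 0.3365. Power is then Φ(0.3365/0.1195 − 1.96) = 0.80, so the figure reproduces. It concerns a drinking-problem count, says nothing about H4, and makes no allowance for missing surveys.

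**Inputs for H4.** From the documents: 20 women per arm (section 14), a baseline-to-post paired test (20a), and knowledge also assessed at 3 months (18a). Assumed, because the documents give no figure: 10% to 40% of post surveys missing, baseline-post correlation 0.3 to 0.7, equal score SDs at the two times, two-sided 5%.

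**Step 1: who is analysed.** The test statistic is t = mean(d) / (SD(d)/√m), where d is post minus baseline and m is the number of women with both scores. The smallest change detectable with 80% power, in SDs of d, is:

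| Missing post | Pairs of 20 (one arm) | Detectable | Pairs of 40 (both arms) | Detectable |
|---|---|---|---|---|
| 0% | 20 | 0.66 | 40 | 0.45 |
| 10% | 18 | 0.70 | 36 | 0.48 |
| 20% | 16 | 0.75 | 32 | 0.51 |
| 30% | 14 | 0.81 | 28 | 0.55 |
| 40% | 12 | 0.89 | 24 | 0.60 |

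**Step 2: bias in the estimated gain.** This was simulated with 20,000 trials per setting, 20 women each, in SDs of the knowledge score. Maximum likelihood here keeps the baseline of women with no post score. The first figure is for 20% missing and correlation 0.5. The range in brackets covers 10% to 40% missing and correlations 0.3 to 0.7.

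| Who misses the post survey | Complete pairs | Maximum likelihood |
|---|---|---|
| Completely at random | 0.00 | 0.00 |
| Women with low baseline knowledge | −0.09 (−0.03 to −0.23) | within 0.01 of zero |
| Women with high baseline knowledge | +0.09 (+0.03 to +0.23) | within 0.01 of zero |
| Women who gain little | +0.17 (+0.06 to +0.44) | +0.13 (+0.05 to +0.31) |

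A further simulation let low app use drive both a small gain and a missed survey (use-gain correlation 0.3 to 0.5, 10% to 40% missing). Complete pairs overstated the gain by 0.03 to 0.21 SD. Likelihood estimation that included app use was within 0.01. Without app use in the model, that bias would be only partly removed.

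**Step 3: precision.** Take correlation 0.5, score SD 1 and 15 of 20 post scores present, with two time points only. The variance of a difference is 2(1 − 0.5) = 1.

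- Full data: 1/20 = 0.050.
- Complete pairs: 1/15 = 0.0667, so the SE ratio to full data is sqrt(0.0667/0.050) = 1.155.
- Maximum likelihood: (1 − 0.5²)/15 + (1 − 0.5)²/20 = 0.75/15 + 0.25/20 = 0.0625, so the SE ratio is sqrt(0.0625/0.050) = 1.118.

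Most of the 15% loss remains, at about 12%.

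**Step 4: complete data.** With a separate mean for each arm at each time, unstructured covariance and no missing scores, the model's estimated means are the raw means. The within-arm change then equals the mean paired difference.

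**The case against.** The strongest reply is that 20c sits under a heading about nonadherence, so its all-participant sentence may mean only that non-adherers are not excluded. A paired test on everyone who answered both surveys, adherent or not, fits that reading. H4 is also defined as a baseline-to-post change, so leaving out 3-month scores is not itself a fault. The study is a feasibility pilot of 40 women with exploratory tests.

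Much of this stands, and it limits how much the point matters. It does not remove the conflict with the maximum-likelihood sentence, which is general and which a paired t-test cannot follow.

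Three stronger readings are tempting but unsupported.

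- **A breach of intent to treat.** A reader might infer one. Section 20c defines the term by group membership: "We will use an intent to treat analysis, in which participants will be retained in the group to which they were originally randomized". H4 as written is a within-person change with no stated arm contrast, and a missing score moves nobody between groups.
- **A test restricted to women who did not drop out.** That is not the analysed set. A woman who stops the app but answers the separately paid and prompted post survey is included. One who skips the post survey but returns at 3 months is not.
- **A known overstatement of learning.** One could suppose that completers gain 2.0 items and the missing 25% would have gained 0.5. The true mean is then 0.75×2.0 + 0.25×0.5 = 1.625, a 23% overstatement. Every input is invented. No section says that early stoppers are likelier to miss the post survey. Controls have no skills activities (11a), so that account would not apply to them. Maximum likelihood would not return 1.625 either, unless observed data predicted the unseen gains.

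**Conclusion.** The mismatch is real and can be read directly from 20a and 20c: H4 is assigned a complete-pair method under a general rule that calls for all participants and maximum likelihood. Neither the size nor the direction of any bias can be found from the documents. Under the assumed settings it is about 0.03 to 0.23 SD in either direction when missingness depends on baseline knowledge, and nil when surveys are missed completely at random. The case for change rests on missingness being related to something the trial observes. If low gainers leave for unrecorded reasons, the likelihood model reduces the bias without removing it. The gain in precision is small. In an exploratory pilot the consequence is modest, but the affected quantity is the one that Aim 4 mainly relies on, and the correction is cheap.

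**What to change.** In section 20a, replace the paired t-test as the main H4 analysis with a likelihood-based repeated-measures model of knowledge score at baseline, post and 3 months. Use unstructured covariance and terms for arm, time and arm-by-time. Include every randomised participant with any knowledge score. Report the baseline-to-post change within each arm, so that the intervention-arm gain is not averaged with controls who saw no skills content.

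Keep the paired t-test as a labelled complete-pair sensitivity analysis, and report the number of missing post scores by arm. In the intervention arm only, a further sensitivity analysis can add days of activity completed as an auxiliary variable. Controls have no activities to count.

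The cost is a few sentences of text. Mixed models are already planned for H5, and the knowledge scores and activity data are already to be collected. The downside is reliance on missingness depending on observed data, which the text should state. If the sponsor prefers to keep the paired test as the main analysis, 20c should say that H4 is an exception.
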